Moreover, we will focus on cognitive control and affective biases therein, because this process is related to RNT. We will measure two major constituents of cognitive control, i.e. working memory processing and motivational biases of cognitive control (with respectively a working-memory update/ignore emotion task and Pavlovian-to-instrumental transfer task) before and after MBCT/waitlist. We will use this behavioural data to assess whether working memory and motivational biases are indeed (i) related to RNT and MDD, (ii) are changed by MBCT and (iii) whether these changes are related to clinical effects of MBCT.

Additionally, we aim to investigate the timing of change by administering weekly self-report questionnaires.

Section 3: Study Methods

Design

Patients will be assigned to intervention (MBCT + TAU) or waitlist (TAU) based on regular clinical assessment procedure and start of treatment groups. The intervention group performs measurements once before (T0), halfway (T1), and once after MBCT (T2), whereas the waitlist performs measurements once before (T0), once during (T1), and once after a waiting period (T2) of at least 7 weeks, but preferably 8-10 weeks. The wait-list group receives MBCT after this waiting period and subsequently performs measurements halfway (T3) and after MBCT (T4).

Sample size – power calculation

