Before start of the study, a sample size calculation for the primary analysis (mediation analysis) was conducted using the Monte Carlo Power Analysis Application provided by Schoemann, Boulton, & Short (2017) (https://schoemann.shinyapps.io/mc_power_med/). This tool enables the researcher to calculate a required sample size for (simple) mediation models by using correlations between the independent variable (IV), dependent variable (DV), and mediator (M). We based the required sample size for the mediation analysis on previously published data on the effectiveness of MBCT for chronic, treatment-resistant depressed patients (Cladder-Micus et al., 2018). We based the calculation on 1000 replications, 20000 Monte Carlo Draws per replication, and a Confidence Level of 95%. The correlation between IV (condition; MBCT + TAU versus TAU) and DV (residual change in depressive symptom; $r = .18$), IV and mediator (residual change in RRS brooding score; $r = .27$), and mediator and DV ($r = .26$) were entered in the application. Based on this calculation, 174 participants would be required. Based on previous studies reporting a drop-out between 10% (Van Aalderen et al., 2012) and 24.5% (Cladder-Micus et al., 2018), we therefore expected a drop-out of 15% and aimed to include 200 participants.

Statistical analysis

Clinical effects of MBCT: replication and assessment of moderation

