To compare the intervention (MBCT + TAU) with the waitlist-control (TAU only) group on sociodemographic, outcome, and hypothesized mediating and moderating variables, independent-samples t-test or chi-square test will be used. The effect of treatment (MBCT + TAU versus TAU) will be tested in the intention-to-treat sample using latent growth curve models (LGCM; (Duncan & Duncan, 1995)). The intercept (baseline score of dependent variable) and slope (representing change over time) will be modeled as latent variables from data at pre-treatment (T0), mid-treatment (T1) and post-treatment (T2) (see Figure 1). First, unconditional models will be estimated separately in each group (MBCT + TAU versus TAU) to test whether a linear (0, 4 and 8 weeks) or non-linear trend of change over time would fit the data best. Second, group (MBCT + TAU = 1 ; TAU = 2) will be added to the model as predictor of the latent growth factors. The path from Group to Slope reflects differences in the trajectories of change on the outcome measure(s) between groups whereas the path from Group to Intercept reflect baseline differences on outcome measures. To assess the rate of change within each group, within-subject cohens d effect sizes will be calculated by dividing the mean-difference (T2-T0) by the standard deviation (SD) of the difference, with 0.2, 0.5, 0.8 representing small, medium and large effects respectively. To compare the rate of change between groups, a between group effect size for growth modeling analysis (GMA) will be calculated using the following equation:
$$\frac{\beta_{11} \times \text{time}}{\text{Pooled SD raw scores}}$$

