 (Feingold, 2009), in which β_{11} is the difference between the means of the unstandardized slopes of the MBCT + TAU versus TAU group. β_{11} must be multiplied by time (in our case 8) to obtain the difference between the model-estimated means of both groups at the end of the study (adjusted for baseline differences). Third, potential moderators of treatment effect, such as baseline levels of different measures of RNT, will be added as predictor of the latent growth factors. A significant interaction effect between moderator, group and slope would mean a moderated treatment effect. As a sensitivity analysis and as a basis for the analyses regarding mechanisms of change (for which a minimal effective MBCT-dose is a requisite), the LGCM analyses will be repeated in the per protocol sample (minimal effective dose of ≥ 4 sessions (Teasdale et al., 2000)).

[figure not shown]

Figure 1. Structure of the Latent Growth Curve Models (LGCM) for the different outcome measures that were assessed before (T0), mid-way (T1) and after (T2) treatment. First unconditional models will be run (blue part). Subsequently a conditional model will be run, with group (MBCT + TAU versus TAU) as predictor of the latent growth factors (yellow).

Mediation analyses

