We will assess whether there are differences between healthy controls (HC) and remitted and currently depressed MDD patients by incorporating a factor Group with three levels.

To further answer whether the update and ignore processes are related to rumination and/or depressive symptoms we will add these scores separately to the models described above with only the MDD patients. Any significant interaction with one of these covariates would indicate a relation between emotion dependent WM processing and rumination or depressive symptom severity.

We will report effects significant at an alpha-level of $<.05$. Any significant higher order interactions will be analysed using post-hoc simple interactions for ease of interpretation.

Control analyses WMUIET

As sensitivity analyses we will conduct a number of control analyses that confirm the robustness of the results: we will assess the lack of effect of covariates of no interest, including age and gender.

3. Weekly self-report questionnaires

The weekly self-report questionnaires will be administered after each MBCT session (8 times) and on a weekly basis in the wait-list control group. We will use these measurements for exploration of the (variation in the) timing of individual change processes.

References

Barr, D. J. (2013). Random effects structure for testing interactions in linear mixed-effects models. *Front Psychol*, 4, 328. <https://doi.org/10.3389/fpsyg.2013.00328>

Barr, D. J., Levy, R., Scheepers, C., & Tily, H. J. (2013). Random effects structure for confirmatory hypothesis testing: Keep it maximal. *J Mem Lang*, 68(3). <https://doi.org/10.1016/j.jml.2012.11.001>

Cladder-Micus, M. B., Speckens, A. E., Vrijen, J. N., T. Donders, A. R., Becker, E. S., & Spijker, J. (2018). Mindfulness-based cognitive therapy for patients with chronic, treatment-resistant depression: A pragmatic randomized controlled trial. *Depression and anxiety*, 35(10), 914-924.

Dai, Q., & Feng, Z. (2009). Deficient inhibition of return for emotional faces in depression. *Progress in Neuro-Psychopharmacology and Biological Psychiatry*, 33(6), 921-932.

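### The linear growth model dates T2 at week 8 in both arms although the waitlist T2 may fall from week 7 onwards; if mean timing differs by arm, the group difference in slope can be biased

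*SAP*

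**What the plan says.** In the SAP section on clinical effects of MBCT, the treatment effect is tested with a latent growth curve model on T0, T1 and T2. Unconditional models are first fitted in each group "to test whether a linear (0, 4 and 8 weeks) or non-linear trend of change over time would fit the data best". Group then "will be added to the model as predictor of the latent growth factors", so a single set of time scores serves both arms. For the between-group effect size, the slope difference "must be multiplied by time (in our case 8) to obtain the difference between the model-estimated means of both groups".

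The Design paragraph of Section 3 ties T2 to a different event in each arm. For MBCT it reads "The intervention group performs measurements once before (T0), halfway (T1), and once after MBCT (T2"), with no window in weeks. For the waitlist, T2 comes "once after a waiting period (T2) of at least 7 weeks, but preferably 8-10 weeks", and no latest date is given. The same paragraph says that assignment follows the regular clinical assessment procedure and the start of treatment groups, so it is not randomised.

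The SAP does not mention actual assessment dates, individually varying time scores, group-specific loadings or a sensitivity analysis for visit timing.

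**The concern.** The preferred waitlist window starts at the modelled value of 8 weeks and otherwise lies above it. The intervention T2 follows a course of eight sessions; the weekly questionnaire section says "The weekly self-report questionnaires will be administered after each MBCT session (8 times"). Since one visit is tied to the end of a course and the other to the end of a wait, average elapsed time may differ by arm, and this would not be only random scatter.

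If it does differ, any steady change in the waitlist is spread over the wrong number of weeks. The path from group to slope then mixes the treatment effect with the difference in follow-up time. This path is the test of main objective (i), replication of the MBCT effect on symptoms and repetitive negative thinking, and the moderator analyses use the same slopes. Spread of T2 dates within the waitlist would also add to the apparent variance of the slopes.

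**Working it through.** **Inputs from the SAP.** Time scores 0, 4, 8 and multiplier 8 (section on clinical effects of MBCT); waitlist T2 from 7 weeks, preferably 8 to 10 (Design); waitlist T1 half-way (Objectives).

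**Assumptions, because the SAP gives no figures.** Waitlist change is linear at s SD per week; total improvement is 0.1 to 0.3 SD per 8 weeks; the intervention T2 falls at week 8 on average.

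**Step 1: the plan's own figure.** The multiplier 8 is the last linear time score. Slope difference x 8 therefore returns the modelled difference at T2. The two statements agree with each other.

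**Step 2: fitted waitlist slope.** Let the waitlist be measured at weeks 0, w/2 and w, so that its mean changes are 0, s·w/2 and s·w. The centred time scores are -4, 0 and 4, so the least-squares slope is

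4·(s·w - 0) / (16 + 0 + 16) = s·w/8.

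With T1 half-way, the three means lie exactly on a line with that slope. With T1 at week 4 the least-squares result is the same, because the middle score is zero after centring. The relative error is w/8 - 1.

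**Step 3: effect on the group difference.** With the MBCT arm at week 8, the error in (slope difference x 8) is -8s·(w/8 - 1), that is, the waitlist's own 8-week change times the relative error, with the sign reversed.

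| Mean waitlist T2 | Error in waitlist slope | Shift, 0.1 SD improvement | Shift, 0.3 SD improvement | Direction |
|---|---|---|---|---|
| 7 weeks | 7/8 - 1 = -12.5% | 0.0125 SD | 0.0375 SD | in favour of MBCT |
| 8 weeks | 0 | 0 | 0 | none |
| 9 weeks | 9/8 - 1 = +12.5% | 0.0125 SD | 0.0375 SD | against MBCT |
| 10 weeks | 10/8 - 1 = +25% | 0.025 SD | 0.075 SD | against MBCT |

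Example: at 10 weeks with 0.3 SD, 0.3 x 0.25 = 0.075 SD.

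**Step 4: when the shift vanishes.** If s = 0, every entry is zero. If change has levelled off before the T2 visits, the extra weeks add nothing. If both arms have the same mean T2 at week w, both slopes are multiplied by w/8: the test of group on slope is unchanged and the T2 contrast is intact, and only its label as an 8-week difference is off.

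**The case against.** The strongest reply is that no difference in timing between arms has been shown. T0 precedes the course and T2 follows it, so eight weekly sessions may well take more than 8 weeks from T0 to T2. The preferred waitlist window may have been chosen to match. This stands: the SAP gives no window for the intervention T2, and the table depends on placing it at week 8.

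Coding waves by event is also conventional, and the 0/4/8 scores belong to the linear candidate only. That is fair, but a non-linear shape shared by both arms would not restore different elapsed times, and nothing in the SAP says that it would use actual weeks.

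Three stronger readings are tempting and are not supported:

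- *The plan biases the slope difference.* Neither the waitlist trend nor the visit dates are in the SAP, so neither the existence nor the sign of a bias is established. With an improving waitlist seen after week 8, the error is conservative. Regression to the mean need not keep growing between weeks 8 and 10, so it does not fit the proportional formula.
- *The waitlist T1 is undated too.* Design says only that it falls during the wait, but Objectives places it half-way.
- *The shift is a large share of the planned effect.* The correlation in the sample size section ("residual change in depressive symptom; $r = .18") refers to residual change, whereas the growth-model effect size divides by the pooled raw-score SD. The two scales should not be mixed. A mean T2 beyond 10 weeks is permitted, but the SAP gives no figure for it.

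**Conclusion.** The mismatch between fixed time scores and an open waitlist window is real, and the SAP does not deal with it. It can bias the group difference in slope only if mean elapsed time to T2 differs between arms and the waitlist is still changing at that point. Under the stated assumptions the shift is about 0.01 to 0.04 SD at a mean waitlist T2 of 9 weeks, and 0.025 to 0.075 SD at 10 weeks, the upper end of the preferred range. Both are against MBCT if the waitlist improves. The direction reverses if the waitlist worsens, or if it improves and is seen at week 7.

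This concerns the growth-curve analyses of treatment effect and moderation. A reader might infer that the mediation result is affected as well, but this working does not show it: the primary mediation analysis is a wave-based cross-lagged model that uses neither these time scores nor the factor 8. Severity is minor to moderate.

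**What to change.** In the growth-curve section, replace the common scores by each participant's actual weeks since T0 as individually varying time scores, or use the equivalent mixed growth model, and evaluate the group difference at 8 weeks. Report the distribution of T1 and T2 timing by arm. Keep the fixed 0/4/8 model for comparing linear with non-linear shapes and as a sensitivity analysis.

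The visit schedule stays as it is; the change needs only SAP wording and the assessment dates. The price is that conventional absolute fit indices are not available for the individually timed model, which is why the fixed model should be retained alongside it.

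### Is the fixed multiplier of 8 in the between-group effect size wrong if a non-linear growth form is chosen?

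*SAP*

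**What the plan says.** All of this stands in the SAP under Clinical effects of MBCT: replication and assessment of moderation.

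- **Model.** The "intercept (baseline score of dependent variable) and slope (representing change over time) will be modeled as latent variables", using the three waves T0, T1 and T2. The text refers to Figure 1 for the diagram, captioned "Structure of the Latent Growth Curve Models (LGCM) for the different outcome measures".
- **Choice of time form.** First, "unconditional models will be estimated separately in each group", to see whether a "linear (0, 4 and 8 weeks) or non-linear trend of change over time would fit the data best". Group is then added as a predictor of the growth factors.
- **Effect size.** The between-group measure is β11 × time, divided by the pooled SD of raw scores. Here β11 "is the difference between the means of the unstandardized slopes of the MBCT + TAU versus TAU group", and it "must be multiplied by time (in our case 8) to obtain the difference between the model-estimated means of both groups at the end".

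Loadings are written out for the linear form only. The text does not name the non-linear form or the criterion for choosing between the two.

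**The concern.** β11 is unstandardized, so its size depends on how the slope factor is scaled, and the scale is set by the loadings. The SAP opens a non-linear branch without giving its loadings, yet fixes one multiplier for every case. If the non-linear form were scaled so that the T2 loading is not 8, multiplying by 8 would no longer give the group difference at T2.

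At stake is the only between-group effect size that the SAP defines for its first objective, the replication of benefit. The choice of form arises for each outcome measure and again in the per-protocol repeat, so values for different outcomes or samples could end up on different scales. A moderate distortion, such as -0.56 in place of -0.40, would not look odd in a results table.

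**Working it through.** **Inputs from the SAP.** Linear loadings 0, 4, 8; multiplier 8; one intercept factor and one slope factor; three waves.

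**Assumed inputs (not in the SAP).** True group difference in T0-to-T2 change D = -0.40 SD; share f of that change reached by week 4, taken as 0.4, 0.5, 0.6 or 0.7.

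**1. The plan's own figure.** With T2 slope loading λ2, the model-implied group difference at T2, net of the intercept difference, is λ2 × β11. For loadings 0, 4, 8, λ2 = 8. The stated multiplier is reproduced.

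**2. Which non-linear forms three waves allow.** Three means plus six variances and covariances give 9 observed moments.

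| Form | Parameters |
|---|---|
| Linear | 2 means + 3 factor (co)variances + 3 residual variances = 8 |
| One slope, one freed loading | 8 + 1 = 9 |
| Full quadratic | 3 + 6 + 3 = 12 |

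The full quadratic has more parameters than moments. A single slope with one freed loading is therefore the likely non-linear form. The remaining question is which loading is freed and which one sets the scale.

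**3. T1 loading freed, T2 held at 8 (0, free, 8).** Then β11 = D/8, and 8 × β11 = D = -0.40 for every f. The multiplier is exact.

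**4. T2 loading freed, T1 held at 4 (0, 4, free).** Then β11 = fD/4 and λ2 = 4/f. Multiplying by 8 gives 8fD/4 = 2fD.

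| f | λ2 = 4/f | 8 × β11 | λ2 × β11 |
|---|---|---|---|
| 0.4 | 10 | -0.32 | -0.40 |
| 0.5 | 8 | -0.40 | -0.40 |
| 0.6 | 6.67 | -0.48 | -0.40 |
| 0.7 | 5.71 | -0.56 | -0.40 |

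This is the same curve as in step 3 with the slope factor rescaled. Only the conversion constant differs.

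**5. T2 loading set to 1 (0, free, 1).** Multiplying by 8 would give 8 × (-0.40) = -3.20, an error that would be obvious on sight.

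**6. Which scaling the text supports.** Time is coded in weeks with T2 at week 8. The formula takes time as 8, and its declared purpose is the group difference in model-estimated means at the end of the study. Of the forms in steps 3 to 5, only 0, free, 8 satisfies all three statements. The text mentions none of the other scalings.

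**7. Arms that select different forms.** Group enters one conditional model as a predictor, which implies one set of loadings for both arms. With an assumed waitlist change of -0.2 SD and D = -0.40, five pairs of differing arm shapes under 0, free, 8 gave 8 × β11 between -0.40 and -0.43. A common form therefore costs at most 0.03 SD in these cases.

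**The case for a change.** The strongest case for acting is that a prespecified rule should be right as written. The SAP says the slope difference must be multiplied and gives a number, with no exception for the branch that it opens itself.

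Nor is that branch remote. Comparing linear with a freed loading is a 1-df comparison. Even with truly linear change in both arms, at least one arm would select non-linear with probability 1 - 0.95² = 0.0975 under a 5% likelihood-ratio test. Under AIC the per-arm chance is 0.157, so the figure is 1 - 0.843² ≈ 0.29. In simulations with an assumed 100 patients in one arm and a 0.6 SD change, non-linear was selected in 16-17% (test) or 32-34% (AIC) of runs at f = 0.4 or 0.6, and in 50% or 70% at f = 0.7. One sentence would close the gap.

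Part of this stands: the visible text does not write down the non-linear loadings or the selection criterion. The rest does not carry the conclusion. Those probabilities are for choosing any non-linear form. The error also needs a scaling with a T2 loading other than 8, and then the use of 8 against the formula's stated purpose. No probability is available for that step, and under 0, free, 8 the error is zero however often non-linear is chosen. The figures for truly linear change belong to f = 0.5, where even 0, 4, free returns -0.40 at population level. The selection rules, sample size and shapes are assumptions, not SAP content.

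**Conclusion.** No change to the plan follows. The multiplier of 8 is correct for the linear form and for the non-linear form most consistent with the SAP's wording. What is left unsaid is a modelling detail that an analyst working to the stated purpose would fill correctly, because the target quantity, the group difference at T2, is named.

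If the detail were filled badly, with loadings 0, 4, free and a multiplier of 8, an assumed -0.40 SD would be reported as -0.32 to -0.56 for f between 0.4 and 0.7. That would touch one descriptive effect size. The multiplier is applied after the model is fitted, so the test of the Group-to-Slope path does not depend on it, and the primary mediation analysis uses a different model. The planned within-group T2-T0 effect sizes also give a rough check against which a misscaled value could be noticed.

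The conclusion assumes a single slope factor, as the text describes, and a common time form in the conditional model. Figure 1 is not reproduced in the text available here. If it shows a T2 loading of 8, the point disappears altogether. If it showed another scaling for the non-linear form, the multiplier would need a second look.

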Elucidating these mechanisms will provide insight in the existing individual differences in effectiveness of MBCT. Consequently, this insight will help to improve effectiveness of treatment and even personalize treatment regimes. One likely candidate that could play a major role in the positive effects of MBCT on depressive symptoms, is repetitive negative thinking (RNT) (van der Velden et al., 2015). Depressive rumination is the most well-studied form in the context of depression and has been described as the process of thinking perseveratively about one's feelings and problems (such as symptoms of depression) and their possible causes and consequences (Nolen-Hoeksema et al., 2008). It is believed that during MBCT participants develop the ability to become aware of automatic maladaptive cognitive processes such as depressive rumination, and learn to decenter and disengage from them (Segal et al., 2013). Because of this core skill to be learned during MBCT patients may be prevented to enter a vicious cycle of ruminative thinking that could otherwise aggravate symptoms of depression or have resulted in a new depressive episode.

Objectives

Our main objectives are (i) to replicate the beneficial effects of MBCT on depressive symptoms and RNT in patients with chronic or recurrent depression (crMDD), and (ii) to investigate whether individual levels of RNT (iia) mediate and/or (iib) moderate the MBCT-induced reduction in depressive symptoms.

To this end self-report questionnaires of depressive symptoms, content-independent RNT and depressive rumination will be administered before, half-way and after MBCT (intervention group) or before, half-way and after a waiting-period (waitlist group).

Secondary objectives

To triangulate research findings we will administer an experimental task (breathing focus task) that measures intrusive thoughts during task performance.

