Problems in motivation, reward and punishment processing and approach and avoidance behaviors have been central to cognitive-behavioral theories on depression (MDD) (see for reviews: Trew, 2011; Chen et al., 2015; Huys et al., 2015). The PIT paradigm therefore seems exceptionally suited to deliver rich behavioral information on the (individual variation of) affective-cognitive aspects relevant to depression in addition to for example questionnaire data. Indeed, two studies investigated PIT within MDD samples (Huys et al., 2016; Nord et al., 2018). Both studies find that MDD patients do not differ from healthy controls in the acquisition of instrumental contingencies (based on reward and punishment reinforcement learning) or Pavlovian contingencies (based on passive classical conditioning). However, in both studies the action specific PIT effect differs from HC, but in opposite directions: Nord et al. (2018) show that MDD patients show enhanced action-specific aversive PIT (i.e. the difference between the effect of an aversive CS on approach vs withdrawal actions), whereas Huys et al. (2016) show that MDD patients do show PIT in approach context, but that action-specificity is disturbed. Moreover, Nord et al. found a positive relation across (but not within) groups between depression symptom severity and action-specific aversive PIT, whereas Huys et al. found a negative relation between depression scores and action specific PIT within the patient sample. Moreover, Huys et al. found that action-specificity was related to improvement of depressive symptoms across 4-6 months.

Notably, explanation of these equivocal findings might contribute substantially to understanding the (cognitive-behavioral) variation within the heterogeneous MDD population. This might extend to the observed differences in populations recruited in these studies: Where Huys et al. included also MDD patients using psychotropic medication, Nord et al. did not. Here we set out to contribute to understanding these differences and extend our knowledge on PIT in MDD by addressing the following research questions:

- (1) First, we ask how, especially aversive, PIT differs between healthy controls, MDD patients with a current depressive episode or in remission.

(2) Second, within the MDD sample, we ask how depressive symptoms are related to PIT. We will explore the role of medication status on PIT in the MDD sample.

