between- and within-subject variability these data will be analysed with logistic mixed-level models using the lme4 package in R (Bates et al., 2014). Reflecting our objectives, the mixed models will include where appropriate the within-subject factors treatment (MBCT, waitlist), Action Context (approach vs. withdrawal) and Valence Context (appetitive/neutral/aversive), and the between-subject factors Group (HC, MDDremitted, MDDcurrent), medication status (serotonergic/catecholaminergic medication, no medication) and depressive symptom severity (in terms of IDS-SR score) or rumination (in terms of RRS brooding score). Models include all main effects and interactions. All models will contain a full random effects structure (Barr et al., 2013). When the full random effects structure prevents the models to converge, we will make amends.

Planned contrasts involve those contrasts focusing on action-specific aversive PIT, i.e. those interaction including an interaction between Valence Context (neu, aversive) x Action Context (approach, withdrawal). Next to the planned contrasts we will explore the full model. Thus, models relating to the different research questions will be:

(1) Valence Context * Action Context * Group + full random effects structure

MDD sample:

(2) Valence Context * Action Context * IDS-SR + random effects structure

(3) Valence Context * Action Context * IDS-SRchange + random effects structure

(4a) Time * Valence Context * Action Context * Treatment + random effects structure

(4b) Time * Valence Context * Action Context * Treatment * IDS-SRchange + random effects structure.

We will report effects significant at an alpha-level of $<.05$. Any significant higher order interactions will be analysed using post-hoc simple interactions for ease of interpretation.

Control analyses PIT

As sensitivity analyses we will conduct a number of control analyses that confirm the robustness of the results: we will assess the i) lack of effect of covariates of no interest, including age, gender, intelligence; ii) robustness of the results to exclusion of participants with deterministic PIT

responding; iii) successful instrumental conditioning, where we will also assess the influence of the degree of instrumental conditioning, and iv) Pavlovian conditioning on the main results.

[figure not shown]

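### The moderation test for objective (iib) cannot separate RNT from baseline severity, because no severity-by-group term is planned beside RNT-by-group in a sample of remitted and currently depressed patients

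*SAP*

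**What the plan says.** Main objective (iib), under Objectives, is to find out whether individual levels of RNT "moderate the MBCT-induced reduction in depressive symptoms". The test is the third step of the latent growth curve analysis in the section on clinical effects of MBCT. There, "potential moderators of treatment effect, such as baseline levels of different measures of RNT, will be added as predictor of the latent growth factors", and the decision rule is: "A significant interaction effect between moderator, group and slope would mean a moderated treatment effect".

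The treatment effect "will be tested in the intention-to-treat sample using latent growth curve models", with a per-protocol repeat. Nothing restricts or stratifies these models by episode status. Baseline severity enters only through the growth model itself: "The intercept (baseline score of dependent variable) and slope (representing change over time) will be modeled as latent variables". Group predicts both growth factors, but no path lets the group effect on slope differ by intercept.

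The mix of patients is described in the task sections. The first PIT research question concerns "MDD patients with a current depressive episode or in remission". The PIT models use "the between-subject factors Group (HC, MDDremitted, MDDcurrent", with healthy controls as the third level. The WMUIET analysis compares healthy controls with "remitted and currently depressed MDD patients by incorporating a factor Group with three levels".

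**The concern.** The introduction says the purpose is to understand why patients differ in their response to MBCT, to improve treatment and to personalise it. That requires knowing whether RNT itself marks the patients who benefit or only stands in for how depressed they are at baseline.

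Patients in remission may have less room to improve on the IDS-SR. The SAP itself links rumination to depressive symptoms, so baseline RNT may be partly a severity marker. If both hold, part of any severity-by-group effect will load onto RNT-by-group, because the model contains no severity-by-group term to take it up. The latent intercept does not help: it adjusts for starting level but leaves the treatment effect constant across starting levels. The per-protocol repeat has the same structure. The SAP does use episode status elsewhere: its third PIT question is confined to currently depressed patients. The moderation analysis has no counterpart.

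A significant result could then be written up as evidence for RNT as a specific moderator when the data show only that more symptomatic patients improved more.

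**Working it through.** **The SAP's own figure.** The only sample size given is for mediation: 174, from correlations .18, .27 and .26. A Monte Carlo check of the indirect effect gives 81.4% power at 174, so the figure reproduces if the target was 80% (an assumption, since the SAP states none). No figure is given for moderation, so the size of the problem has to be worked out under assumptions.

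**Inputs from the SAP.**
- Condition-outcome correlation r = .18 (sample size section). At 1:1 allocation, d = 2r/√(1 − r²) = 0.36/0.984 = 0.366 within-group SDs of change.
- N after 15% drop-out: 200 × 0.85 = 170.
- Test level .05.

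**Assumed inputs (not in the SAP).**
- Share remitted p = 40%.
- Mean IDS-SR 36 (current) and 18 (remitted), within-class SD 8, so overall SD = √(64 + 0.4 × 0.6 × 18²) = √141.8 = 11.9.
- SD of change 9.
- Correlation ρ of baseline RNT with severity: .3, .5 or .6.
- No benefit in remission, and no role of RNT beyond severity.

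**Step 1: effect in current patients.** The average effect is 0.366 × 9 = 3.29 points. If it falls wholly on the 60% who are currently depressed, their effect is 3.29/0.6 = 5.49 points.

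**Step 2: RNT-by-group coefficient induced by severity alone**, per SD of RNT: ρ × Δ × p(1 − p) × 18/11.9, where Δ is the difference in effect between the classes. With Δ = 5.49 this is ρ × 1.99, or 0.60, 1.00 and 1.19 points.

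**Step 3: chance of significance.** The approximate standard error is 2 × 9/√170 = 1.38. The ratios are 0.43, 0.72 and 0.87, and P(|Z| > 1.96) is about 7%, 11% and 14%. Simulating the same set-up (change regressed on group, RNT and their product; 10,000 trials per setting) gives slightly lower values, because uneven benefit adds residual variance:

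| Effect, current / remitted (points) | ρ = .3 | ρ = .5 | ρ = .6 |
|---|---|---|---|
| 5.49 / 0 (average implied by r = .18) | 7% | 10% | 13% |
| 8 / 0 | 9% | 16% | 22% |
| 7 / 1 | 8% | 12% | 14% |
| 6 / 3 | 6% | 7% | 7% |
| 5 / 5 (no dependence on severity) | 5% | 5% | 5% |

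Other runs of the first two rows gave 8% to 13% and 9% to 25%. With severity-by-group or episode-status-by-group added, every setting returns to about 4% to 6%.

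**Step 4: share remitted.** At the r = .18 effect, 20% remitted gives 6% to 7%, and 50% gives 8% to 17%.

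**Step 5: three-wave version.** Individual slopes over weeks 0, 4 and 8, with outcome reliability .85, N = 174 and 40% remitted, gave 8%, 14% and 19%. That run set the average effect to 0.366 *baseline* SDs. Its SD of change is √(0.25 + 2 × 0.15/0.85) = 0.78, so the effect is 0.366/0.78 = 0.47 SDs of change, larger than r = .18 implies. The first table row is the closer match to the SAP.

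**Step 6: price of adjustment.** With a true RNT moderation of 3 points per SD and no severity dependence, power for RNT-by-group is about 57% unadjusted. With severity-by-group added it is about 45% (ρ = .5) and 39% (ρ = .6); with episode-status-by-group alone, 50% and 47%.

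**The case against.** The strongest reply is that the unadjusted test answers the question as written. Objective (iib) asks whether RNT levels moderate the benefit, not whether they do so independently of severity. In the settings above, benefit really does differ by RNT level, because RNT tracks episode status. Detecting that is correct for marginal effect modification and describes who benefits. This stands: the significant results in the table are errors only if read as a role of RNT beyond severity. A reader might infer that the planned test is invalid, and the SAP does not support that.

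A reader might also infer that a floor effect in remitted patients will occur and that their RNT will be lower. The SAP shows neither. It gives no share remitted, no baseline IDS-SR or RNT values and no baseline correlation between them. The .26 in the sample size section relates change scores, so it cannot support a baseline correlation of .5 or .6. The introduction also presents rumination as a route to a new episode, so it is not described only as a feature of current depression. The mechanism is plausible but conditional.

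The moderator list is open-ended, so severity could be tested too. Testing it in a separate model, however, would not adjust RNT-by-group, and no joint model is promised.

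Finally, resting (iib) on an adjusted model alone would cost power (Step 6). Observed T0 IDS-SR is also already an indicator of the latent intercept, so using it again as a predictor of slope shares measurement error. Both points stand and shape the fix.

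**Conclusion.** The point holds as a limit on interpretation. As planned, a significant RNT-by-group effect cannot distinguish RNT from baseline severity, and the SAP's aim of explaining and personalising response depends on that distinction.

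At the average effect implied by the SAP's r = .18, with 40% remitted, no benefit in remission and ρ from .3 to .6, severity alone makes the test significant in about 7% to 13% of trials. With a larger effect (8 and 0 points) the rate reaches about 22% to 25%. It falls to 6% to 7% when few patients are remitted or remitted patients also benefit, and is about 5% when benefit does not depend on severity. These rates are per RNT measure, and the SAP refers to several. The remitted share, the correlation and the uneven benefit are assumptions, and the mixed sample is read from the task sections because the growth-model section is silent on episode status.

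This is a cheap improvement.

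**What to change.** In the third growth-model step:

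1. Keep the unadjusted RNT-by-group test and label it as a description of who benefits.
2. Prespecify a sensitivity model in which RNT-by-group is entered jointly with baseline severity by group, as latent intercept by group or as episode status by group, with the corresponding main effects. One severity term is enough: under the assumed values IDS-SR and episode status correlate about .74 (18 × √0.24/11.9). Episode status by group is the simpler choice, as that factor is already defined for the task analyses. Latent intercept by group uses more information but needs a latent interaction or multigroup model on three waves.
3. Report both RNT-by-group estimates with intervals. State that RNT moderates the MBCT effect beyond symptom severity only if the joint estimate supports it; otherwise report that RNT and severity cannot be told apart.

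Cost: a few sentences in the SAP, some extra modelling, and a wider interval with lower power for the adjusted term. IDS-SR is measured at T0 and episode status is already a planned factor, so no new data are needed.
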